**Unsolicited Adverse Events**

Unsolicited AEs are all AEs for which the participant is not specifically questioned in the participant diary.

---

For details regarding AESIs, refer to Section [8.3.6](#).

### **8.3.3. Follow-up of Adverse Events, Serious Adverse Events and Adverse Events of Special Interest**

The investigator is obligated to perform or arrange for the conduct of supplemental measurements and evaluations as medically indicated to elucidate the nature and causality of the AE, SAE, AESI, or PQC as fully as possible. This may include additional laboratory tests or investigations, histopathological examinations, or consultation with other health care professionals.

Adverse events, and the special reporting situation of pregnancy, will be followed by the investigator as specified in [Appendix 4](#).

### **8.3.4. Regulatory Reporting Requirements for Serious Adverse Events**

The sponsor assumes responsibility for appropriate reporting of AEs to the regulatory authorities. The sponsor will also report to the investigator (and the head of the investigational institute where required) all suspected unexpected serious adverse reactions (SUSARs). The investigator (or sponsor where required) must report SUSARs to the appropriate Independent Ethics Committee/Institutional Review Board (IEC/IRB) that approved the protocol unless otherwise required and documented by the IEC/IRB. A SUSAR will be reported to regulatory authorities unblinded. Participating investigators and IEC/IRB will receive a blinded SUSAR summary, unless otherwise specified.

### **8.3.5. Pregnancy**

All initial reports of pregnancy in participants or partners of male participants must be reported to the sponsor by the study site personnel within 24 hours of their knowledge of the event using the appropriate pregnancy notification form. Abnormal pregnancy outcomes (eg, spontaneous abortion, fetal death, stillbirth, congenital anomalies, ectopic pregnancy) are considered SAEs and must be reported using an SAE reporting form. If a participant becomes pregnant during the study, a determination regarding study vaccination discontinuation must be made by the investigator in consultation with the sponsor.

Follow-up information regarding the outcome of the pregnancy will be required.

If the partner of a male participant becomes pregnant during the study, follow-up information regarding the outcome of the pregnancy will be requested upon the consent provided by the partner.

### **8.3.6. Adverse Events of Special Interest**

AESIs (including potential AESIs) are significant AEs that are judged to be of special interest because of clinical importance, known or suspected class effects, or based on nonclinical signals. AESIs and potential AESIs will be carefully monitored during the study by the sponsor.

AESIs and potential AESIs must be reported to the sponsor within 24 hours of awareness irrespective of seriousness (ie, serious and nonserious AEs) or causality following the procedure described above for SAEs.

AESIs must be reported using the AESI form in the eCRF using the eCRF completion guidelines.

Specific requirements for the AESI are described below.

### 8.3.6.1. Thrombosis with Thrombocytopenia Syndrome

As described in Section 2.2, TTS has been observed following vaccination with Janssen COVID vaccine and is considered to be an AESI in this study. TTS is a syndrome characterized by a combination of both a thrombotic event and thrombocytopenia. ([American Society of Hematology 2021](#); [Brighton Collaboration 2021](#))

Because this syndrome is rare and not completely understood, all cases of thrombosis and/or thrombocytopenia will be considered a potential case of TTS and should be reported to the sponsor within 24 hours of awareness using the AESI form. Each potential AESI will be reviewed to identify a TTS case. A potential TTS case is defined as:

- Thrombotic events: suspected deep vessel venous or arterial thrombotic events as detailed in Section 10.7, [Appendix 7](#), and/or
- Thrombocytopenia, defined as platelet count below LLN for the testing laboratory

Symptoms, signs, or conditions suggestive of a thrombotic event or thrombocytopenia should be recorded and reported as a potential AESI even if the final or definitive diagnosis has not yet been determined, and alternative diagnoses have not yet been eliminated or shown to be less likely. Follow-up information and final diagnoses, if applicable, should be submitted to the sponsor as soon as they become available.

In the event of thrombocytopenia, study site personnel should report the absolute value for the platelet count and the reference range for the laboratory test used.

For either a thrombotic event or thrombocytopenia, complete blood count including platelet count and a coagulation profile available from participant's medical records should be entered in the eCRF. In case these results are not available at the time of the event report in the eCRF, the study site is required to obtain a complete blood count including platelet count and a coagulation profile. Tests should be performed at the local laboratory. Repeat testing may be requested for confirmation upon sponsor discretion.

Aliquots of serum samples collected for immunogenicity test can be reconverted for participant's safety purposes upon sponsor request.

Refer to [Appendix 2, Table 20](#) for a non-exhaustive list of required tests.

In addition, the sponsor requires additional blood samples to be obtained as soon as possible after the potential AESI onset, either during an ad hoc unscheduled visit or the next scheduled visit, whichever comes first. Refer to [Appendix 2, Table 21](#) for a non-exhaustive list of laboratory tests

that may be requested by the sponsor in case of potential AESI reporting for which these additional samples may be used.

AESIs, including potential AESIs, will require enhanced data collection and evaluation. Every effort should be made to report as much information as possible about the event to the sponsor in a reasonable timeframe. Relevant laboratory results can be entered on the AESI form in the eCRF, using the eCRF completion guidelines.

If the investigator is not the treating physician, every effort should be made to collect the information requested in the form from the treating physician and enter the available information in the eCRF.

If an event meets the criteria for an SAE (Section 10.4.1), it should be reported using the same process as for other SAEs.

### ***Treatment and Follow-up Recommendation***

The medical management of thrombotic events with thrombocytopenia is different from the management of isolated thromboembolic diseases. Study site personnel and/or treating physicians should follow available guidelines for treatment of thrombotic thrombocytopenia (eg, [American Society of Hematology 2021](#); [British Society for Haematology 2021](#); [CDC 2021](#)). The use of heparin may be harmful and alternative treatments may be needed. Consultation with a hematologist is strongly recommended.

### **8.4. Pharmacokinetics**

Pharmacokinetics are not evaluated in this study.

### **8.5. Genetics and Pharmacogenomics**

Genetics and pharmacogenomics are not evaluated in this study.

### **8.6. Biomarkers**

Blood will be drawn at selected timepoints during the study for evaluation of biomarkers (may include, but not limited to RNA-seq including TCR and BCR sequencing) related to vaccine immunogenicity, as indicated in the [Schedule of Activities](#). Analyses of biomarkers may be conducted at the sponsor's discretion and may be reported separately from this study.

### **8.7. Medical Resource Utilization and Health Economics**

Medical Resource Utilization and Health Economics parameters are not evaluated in this study.

## **9. STATISTICAL CONSIDERATIONS**

Statistical analysis will be done by the sponsor or under the authority of the sponsor. A general description of the statistical methods to be used to analyze the immunogenicity and safety data is outlined below. Specific details will be provided in the statistical analysis plan.

## 9.1. Statistical Hypotheses

No formal hypothesis will be tested.

## 9.2. Sample Size Determination

### 9.2.1. Initial Safety Cohort (Cohort 1)

The number of participants chosen for the initial safety cohort will provide a preliminary safety assessment. Participants receiving placebo and participants receiving the Ad26/protein preF RSV vaccine as used in studies VAC18193RSV2001 and VAC18193RSV3001 are included for blinding and safety purposes and will provide additional control specimens for immunogenicity assays.

While mild to moderate vaccine reactions (local injection site, systemic responses) are expected, AEs that preclude further vaccine administration or more serious ones that would limit product development are not anticipated.

Table 13 provides the probability of observing at least one AE in a group of the considered sample size given several true AE rates.

**Table 13: Probability of Observing at Least One AE in a Group of the Considered Sample Size Given Several True AE Rates**

| True AE Rate (%) | Probability of Observing at Least One AE in N Participants (%) |       |       |       |
|------------------|----------------------------------------------------------------|-------|-------|-------|
|                  | N=2                                                            | N=3   | N=4   | N=12  |
| 0.5              | 1.0%                                                           | 1.5%  | 2.0%  | 5.8%  |
| 1                | 2.0%                                                           | 3.0%  | 3.9%  | 11.4% |
| 2.5              | 4.9%                                                           | 7.3%  | 9.6%  | 26.2% |
| 10               | 19.0%                                                          | 27.1% | 34.3% | 71.8% |
| 25               | 43.8%                                                          | 57.8% | 68.4% | 96.8% |
| 50               | 75.0%                                                          | 87.5% | 93.8% | 100%  |

AE = adverse event; N = number of participants.

### 9.2.2. Vaccine Components Selection Cohort (Cohorts 1 and 2)

The objective is to compare immunomarker levels, including virus neutralizing antibody (VNA) levels, of the various combinations of vaccine components (Arms 1a, and Arms 2 to 9) to Arm 1b ( $1 \times 10^{11}$  vp Ad26.RSV-A.preF/150  $\mu$ g RSV-A preF protein), based on the estimated geometric mean titer (GMT) ratios and corresponding 95% confidence intervals (CIs). With a sample size of 55 evaluable participants per arm, and assuming a standard deviation for RSV-A2 VNA of 1.3a on the log2 scale, the precision of the estimated GMTs will be ~0.36 on the log2 scale. To account for approximately 10% dropout, a sample size of 60 participants per arm will be used.

a Based on Day 29 VNA results from study VAC18193RSV1004: Cohort 2, Groups 14+17 and Cohort 3, Groups 19+20

Table 14 shows the estimated 95% CIs for several GMT ratios, assuming a standard deviation for RSV-A2 VNA of 1.3 on the log2 scale for 55 participants for immunogenicity evaluation per arm.

*Note:* Per arm, immunogenicity data from the initial safety cohort (Cohort 1) will be combined with those from Cohort 2 to support vaccine components selection, as applicable.

**Table 14: Estimated 95% CIs, by Observed GMT Ratio of VNA Levels.**

| N per Arm | Observed GMT Ratio | Corresponding 95% CI |
|-----------|--------------------|----------------------|
| 55        | 1                  | [0.71; 1.41]         |
|           | 1.2                | [0.85; 1.69]         |
|           | 1.5                | [1.07; 2.11]         |

CI = confidence interval; GMT = geometric mean titer; N = number of participants.

### 9.2.3. Expanded Safety Cohort (Cohort 3)

The expanded safety cohort (Cohort 3) should provide sufficient safety data on the selected vaccine formulation to support late-stage development if the immunogenicity results of Cohort 2 are satisfactory.

Table 15 shows the probabilities of observing at least one AE in the expanded safety cohort with 150 participants per vaccine formulation, 50 participants receiving placebo, and 50 participants receiving  $1 \times 10^{11}$  vp Ad26.RSV-A.preF/ 150 µg RSV-A preF protein, at given true AE rates. This table shows that the current numbers give a reasonable probability to also observe less frequent events in the active arms in this cohort. Combining the 60 participants from Cohorts 1 and 2 and 150 participants from Cohort 3 for the selected vaccine formulation results in 210 participants for this formulation.

**Table 15: Probability of Observing at Least One Adverse Event in the Expanded Safety Cohort (Cohort 3) at a Given True Adverse Event Rate**

| True AE Rate (%) | Probability of Observing at Least One AE in N Participants (%) |        |        |        |
|------------------|----------------------------------------------------------------|--------|--------|--------|
|                  | N=50                                                           | N=60   | N=150  | N=210  |
| 0.5              | 22.2%                                                          | 26.0%  | 52.9%  | 65.1%  |
| 1                | 39.5%                                                          | 45.3%  | 77.9%  | 87.9%  |
| 2.5              | 71.8%                                                          | 78.1%  | 97.8%  | 99.5%  |
| 10               | 99.5%                                                          | 99.8%  | 100.0% | 100.0% |
| 25               | 100.0%                                                         | 100.0% | 100.0% | 100.0% |
| 50               | 100.0%                                                         | 100.0% | 100.0% | 100.0% |

AE = adverse event; N = number of participants.

The observation of 0 events (eg, SAEs) is associated with 95% confidence that the true event rate is below the rates specified in Table 16 for the considered number of participants.

**Table 16: Upper Limit of the 1-sided 95% CI if no Cases are Observed for Different Sample Sizes**

| Sample Size                | N=50 | N=60 | N=150 | N=210 |
|----------------------------|------|------|-------|-------|
| Upper Limit 1-sided 95% CI | 5.8% | 4.9% | 2.0%  | 1.4%  |

CI = confidence interval; N = number of participants.

### 9.2.4. Revaccination and Durability Cohort (Cohort 4)

The revaccination and durability cohort (Cohort 4) should provide sufficient data on the selected vaccine formulation to support future clinical development. To have approximately 150 participants available per arm for evaluating durability of immune response at end of the 5-year study period, and assuming a dropout rate of 10% per year, approximately 300 participants per arm are needed.

Corresponding arms of Cohort 3 and 4 will be combined (Arm 11a [Cohort 3] + Arm 14 [Cohort 4], and Arm 11b [Cohort 3] + Arm 15 [Cohort 4], respectively) for the evaluation of durability of the immune response. Having 75 participants in Arm 11a and 11b in Cohort 3 requires enrollment of 225 participants in Arms 14 and 15 in Cohort 4. Enrollment of 90 participants in Arm 16 (placebo) results in enrollment of in total 540 participants in Cohort 4. Placebo arms from Cohort 3 and 4, Arm 12 and Arm 16, respectively, will be combined in the analyses, as applicable.

Table 17 shows the probabilities of observing at least one AE for the selected formulation for future clinical development, at given true AE rates. This table shows that the current numbers give a reasonable probability to also observe less frequent events in the active arms in this cohort.

**Table 17: Probability of Observing at Least One Adverse Event for the Selected Formulation for Future Clinical Development, at a Given True Adverse Event Rate**

| True AE Rate (%) | Probability of Observing at Least One AE in N Participants (%) |        |        |        |        |
|------------------|----------------------------------------------------------------|--------|--------|--------|--------|
|                  | N=150                                                          | N=225  | N=300  | N=450  | N=600  |
| 0.5              | 52.9%                                                          | 67.6%  | 77.8%  | 89.5%  | 95.1%  |
| 1                | 77.9%                                                          | 89.6%  | 95.1%  | 98.9%  | 99.8%  |
| 2.5              | 97.8%                                                          | 99.7%  | 99.9%  | 100.0% | 100.0% |
| 10               | 100.0%                                                         | 100.0% | 100.0% | 100.0% | 100.0% |
| 25               | 100.0%                                                         | 100.0% | 100.0% | 100.0% | 100.0% |
| 50               | 100.0%                                                         | 100.0% | 100.0% | 100.0% | 100.0% |

AE = adverse event; N = number of participants.

The observation of 0 events (eg, SAEs) is associated with 95% confidence that the true event rate is below the rates specified in Table 18 for the considered number of participants.

**Table 18: Upper Limit of the 1-sided 95% CI if no Cases are Observed for Different Sample Sizes**

| Sample Size                | N=150 | N=225 | N=300 | N=450 | N=600 |
|----------------------------|-------|-------|-------|-------|-------|
| Upper Limit 1-sided 95% CI | 2.0%  | 1.3%  | 1.0%  | 0.7%  | 0.5%  |

CI = confidence interval; N = number of participants.

### 9.3. Populations for Analysis Sets

Vaccine assignment will follow the as-treated principle.

For purposes of analysis, the following populations are defined:

The Full Analysis (FA) Set will include all participants who received the study vaccine, regardless of the occurrence of protocol deviations. All safety and participant information analyses will be based on the FA Set.

The Per-protocol Immunogenicity (PPI) Set will include all randomized participants who received the planned study vaccine(s) and for whom immunogenicity data are available. Samples taken after a participant experiences a major protocol deviation expected to impact the immunogenicity outcomes will be excluded from the PPI analysis.

The analysis of all immunogenicity endpoints will be based on the PPI Set. For key tables, sensitivity immunogenicity analyses might also be performed on the FA Set.

#### **9.4. Statistical Analyses**

The statistical analysis plan will be finalized prior to sponsor unblinding of the locked database for the primary analysis and it will include a more technical and detailed description of the statistical analyses described in this section. This section is a summary of the planned statistical analyses of the most important endpoints including primary and key secondary endpoints.

##### **9.4.1. General Considerations**

The primary analysis will be performed when all participants in Cohort 1 and Cohort 2 have completed their 28-day post-vaccination visit or discontinued earlier.

Analysis populations are defined in Section 9.3. Planned analyses are defined in Section 9.5.

##### **9.4.2. Participant Information**

For all participants, demographic characteristics (eg, age, height, body weight, body mass index, race, and gender) and other baseline characteristics will be tabulated and summarized descriptively.

##### **9.4.3. Immunogenicity Analyses**

Immunogenicity data of corresponding arms from Cohort 1 and Cohort 2 will be combined in all analyses. Immunogenicity data of corresponding arms from Cohort 3 and Cohort 4 will be combined as applicable.

Continuous variables will be summarized descriptively. For continuous parameters, descriptive statistics of the actual values will be calculated at all timepoints, including geometric mean with 95% CI, median and quartiles, as applicable. Additionally, geometric mean fold rises from baseline and corresponding 95% CIs might be calculated.

For combined primary endpoint data of Cohort 1 and Cohort 2, geometric mean ratios between each active arm and Arm 1b will be calculated at all available timepoints, with corresponding 95% CI, as applicable. For Cohort 3, Arms 11a and 11b will be combined and the active arms will be compared to each other at all available timepoints up to 1 year after vaccination on Day 1, by means of geometric mean ratios with corresponding 95% CI. For durability and revaccination evaluation Arm 11a (Cohort 3) and Arm 14 (Cohort 4) will be combined, Arm 11b (Cohort 3) and Arm 15 (Cohort 4) will be combined, and Arm 12 (Cohort 3) and Arm 16 (Cohort 4) will be combined.

For immunogenicity analyses, baseline is considered as the last assessment pre-vaccination. Graphical representations of immunologic parameters will be made as applicable.

Geometric means per arm, and geometric mean ratios between active arms, with corresponding 95% CIs will be estimated via an analysis of variance (ANOVA) including all active arms, using log-transformed post-vaccination immune parameter response as dependent variable and study arm as independent variable. The means and differences in mean and CIs will be back-transformed (by exponentiation) to CIs around a GMT or geometric mean titer ratio (GMR). This analysis will be performed for all available assays and all time points, separately per assay. Data of the same arms from different cohorts will be combined, as applicable.

As a sensitivity analysis, the ANOVA may also be performed adjusting for the respective baseline titers, by including baseline titer as additional covariate.

For categorical variables, frequency tables will be presented.

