### Expanded Safety Cohort (Cohort 3)

In the expanded safety cohort, approximately 400 participants will be randomized in parallel to 1 of 5 arms (in a 6:3:3:2:2 ratio to Arms 10, 11a, 11b, 12, and 13; [Table 7](#)). No pauses in enrollment for safety assessments are planned. Participants will receive either the selected 2×1 mL formulation based on the results from Cohorts 1 and 2, the selected 1 mL formulation for future clinical development, placebo, or the current Ad26/protein preF RSV vaccine (1×10^11 vp Ad26.RSV-A.preF/150 µg RSV-A preF protein).

Vaccine components evaluated in Cohorts 1 and 2 will be administered as 2 IM injections of 1 mL in the same deltoid muscle. However, once the optimal composition is selected, manufacturing formulation will be adjusted to ensure the administration of a single 1 mL vaccine dose in subsequent cohorts. Participants in Arms 11a and 11b will receive the selected vaccine in a 1 mL formulation and a second injection with placebo (1 mL) for blinding purposes. Cohort 3 thus will compare the 2×1 mL formulation of the selected combination of RSV vaccine components from Cohorts 1 and 2 (Arm 10) with the 1 mL formulation to be used for future clinical development (Arms 11a and 11b) with follow-up for 1 year post-vaccination in a double-blind placebo-controlled fashion. Participants in Arm 13 will receive the current Ad26/protein preF RSV vaccine (1×10^11 vp Ad26.RSV-A.preF/150 µg RSV-A preF protein) in a 1 mL formulation and a second injection with placebo (1 mL) for blinding purposes. Participants in Arms 11a, 11b and 12 will continue the study to assess durability and the effect of revaccination with follow-up up to 5 years post first vaccination. The timing of revaccination (at least 12 months relative to the first dose) will be based on Ad26/protein preF RSV vaccine clinical data.

For a subset of the participants, additional cellular immunogenicity assessments will be performed. This subset will be referred to as the Cellular Immuno Subset and will consist of approximately 240 participants: 40 participants per arm in Arms 10, 12 and 13, and 60 participants per arm in Arms 11a and 11b. The Cellular Immuno Subset will be recruited in study sites that have PBMC collection capability.

VAC18195 (JNJ 64400141/ JNJ 64213175/ JNJ-86051823/ JNJ 78991172)

Clinical Protocol VAC18195RSV1001 Original

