### Revaccination and Durability Cohort (Cohort 4)

In the revaccination and durability cohort, approximately 540 participants will be randomized in parallel to 1 of 3 arms (in a 5:5:2 ratio to Arms 14, 15 and 16; Table 8). No pauses in enrollment for safety assessments are planned. Participants in Arms 14 and 15 will receive the selected formulation for future clinical development on Day 1 and participants in Arm 16 will receive placebo on Day 1. Participants in Arm 14 (revaccination arm) and Arm 16 will receive the selected formulation at the same revaccination timepoint as participants in Arm 11a and 12 of Cohort 3. Participants in Arm 15 will receive placebo at the same revaccination timepoint as participants in Arm 11b of Cohort 3.

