#### 5.3.3. Analysis Methods for the Primary Immunogenicity endpoint(s)

For Cohort 1, 2 and 4 the primary endpoint will be RSV neutralization antibody titers measured for RSV-A and RSV-B. In Cohort 3, RSV neutralization antibody titers are a secondary endpoint.

Data of corresponding arms from Cohort 1 and Cohort 2 will be combined in all analyses. Immunogenicity data of corresponding arms from Cohort 3 and Cohort 4 will be combined as applicable, too.

Descriptive statistics will be used for all arms to analyze the actual values (geometric mean, 95% CI, minimum, maximum, median and quartiles) and fold increase from baseline at all timepoints, as well as the percentage of participants with 2- and 4-fold increases from baseline. Additionally, the RSV-A/RSV-B antibody ratio will be reported by time points and the fold increase of RSV-A/RSV-B antibody ratio from baselines will be calculated at all timepoints.

For combined data from Cohort 1 and Cohort 2, geometric mean ratios for each active arm relatively to control Arm 1a and relatively to control Arm 1b, as well as relatively to each other will be calculated at all available timepoints along with corresponding 95% CI as applicable.

For Cohort 3, Arms 11a and 11b will be combined and the active arms (10, 11a+11b, 13) will be compared to each other at all available timepoints up to 1 year after vaccination on Day 1 by calculating the geometric mean ratios along with corresponding 95% CIs.

For durability and revaccination evaluation analyses, the following arms will be combined and compared to each other for all timepoints:

- Arm 11a (Cohort 3) combined with Arm 14 (Cohort 4);
- Arm 11b (Cohort 3) combined with Arm 15 (Cohort 4);
- Arm 12 (Cohort 3) combined with Arm 16 (Cohort 4).

Geometric means per arm of values for RSV-A, RSV-B and the ratio of RSV-A/RSV-B, geometric mean ratios for RSV-A, RSV-B and the ratio of RSV-A/RSV-B between all active arms along with corresponding 95% CIs will be estimated via an analysis of variance (ANOVA) using log-transformed post-vaccination immuno parameter response as dependent variable and study arm as independent variable. The means and differences in mean and CIs will be back transformed (by exponentiation) to CIs around a geometric mean or geometric mean ratio. This analysis will be performed by time points, separately per parameter. As a sensitivity analysis, the ANOVA may also be performed adjusting for baseline titer, age and sex.

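### Comparisons with the pooled placebo-first set (Arms 12+16) carry about a tenth of any cohort difference, because Cohorts 3 and 4 use different allocation ratios and the ANOVA has no cohort term

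*Protocol*

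**What the plan says.** **Allocation.** Protocol 4.1 randomises Cohort 3 "in a 6:3:3:2:2 ratio to Arms 10, 11a, 11b, 12, and 13" and Cohort 4 "in a 5:5:2 ratio to Arms 14, 15 and 16". Tables 7 and 8 give the sizes: 75, 75 and 50 in Arms 11a, 11b and 12, and 225, 225 and 90 in Arms 14, 15 and 16.

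**Pooling.** Protocol 9.4.3 combines 11a with 14 and 11b with 15, and says of the placebo-first arms: "Arm 12 (Cohort 3) and Arm 16 (Cohort 4) will be combined". SAP 5.3.3 repeats this and adds: "For durability and revaccination evaluation analyses, the following arms will be combined and compared to each other for all timepoints". Comparisons involving the placebo-first set, 12+16, are therefore planned.

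**Model.** Both documents estimate geometric means and their ratios by an ANOVA on log-transformed titres, with study arm as the only independent variable. The protocol puts the active arms into this model, and both documents describe the ratios as being between active arms. The sensitivity model is optional. It adds baseline titre (protocol), or baseline titre, age and sex (SAP).

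**What is absent.** Neither document gives a cohort factor, stratification by cohort, or a check of homogeneity between cohorts for these comparisons. The only qualifier is that arms are combined as applicable.

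**The concern.** Participants are randomised within a cohort. Arms 11a, 11b and 12 are exchangeable at entry, and so are 14, 15 and 16, but nothing makes Cohort 3 exchangeable with Cohort 4. If the cohorts contributed to every pooled set in the same proportion, a cohort difference would cancel. They do not: the placebo-first set has relatively more Cohort 3 participants than the vaccine-first sets. With arm as the only factor, part of any cohort difference is read as an arm effect.

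The documents make some difference plausible, without giving its size:

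- The enrolment periods are not tied together and each cohort has its own 28-day analysis, so calendar time and RSV exposure may differ.
- Site mix may differ. About 60 + 60 + 40 = 160 of the 200 participants in Arms 11a, 11b and 12 belong to the Cellular Immuno Subset, recruited at sites that can collect PBMC. Cohort 4 has no cellular sampling.

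At stake are the geometric mean ratios and 95% CIs that compare a first dose on Day 1 with a first dose on Day X and, on one reading of the SAP, vaccine with placebo before Day X. They use neutralising titres, the Cohort 4 primary endpoint.

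**Working it through.** **1. The plan's own sizes reproduce.**

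- Cohort 3: 400 × (6, 3, 3, 2, 2)/16 = 150, 75, 75, 50, 50. Protocol 9.2.3 also states "50 participants receiving placebo".
- Cohort 4: 540 × (5, 5, 2)/12 = 225, 225, 90.
- Protocol 9.2.4 asks for about 300 per pooled vaccine-first arm: 300 − 75 = 225, in agreement with "Having 75 participants in Arm 11a and 11b in Cohort 3 requires enrollment of 225 participants in Arms 14 and 15 in Cohort 4". The total is 225 + 225 + 90 = 540, in agreement with "Enrollment of 90 participants in Arm 16 (placebo) results in enrollment of in total 540 participants in Cohort 4".

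**2. Cohort 3 share of each pooled set.**

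| Set | Cohort 3 | Cohort 4 | Total | Cohort 3 share |
|---|---|---|---|---|
| 11a+14 | 75 | 225 | 300 | 25.0% |
| 11b+15 | 75 | 225 | 300 | 25.0% |
| 12+16 | 50 | 90 | 140 | 35.7% |

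**3. The leak.** Let d be the difference in mean log2 titre, Cohort 3 minus Cohort 4, taken as the same in every arm. The arm-only contrast of 12+16 with either vaccine-first set is off by

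(50/140 − 75/300) × d = 0.107 × d.

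For 11a+14 versus 11b+15 the weight is 75/300 − 75/300 = 0. A least-squares fit with d = 1 returns 0.107 without a cohort term and 0 with one.

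**4. Precision.** The SD of 1.3 log2 is in Protocol 9.2.2, for RSV-A2 titres in Cohorts 1 and 2. It reproduces Table 14: the 97.5% t quantile on 108 df × 1.3 × √(2/55) = 0.491 log2, giving [0.71; 1.41] at a ratio of 1. Assuming the same SD here, SE = 1.3 × √(1/300 + 1/140) = 0.133 and the half-width is 1.96 × 0.133 = 0.261 log2.

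**5. Size over an assumed range of d.** Coverage is a normal approximation at full enrolment.

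| Assumed d (log2) | Leak 0.107 × d | GMR factor | Leak / half-width | Coverage of 95% CI |
|---|---|---|---|---|
| 0.25 | 0.027 | 1.019 | 10% | 94.5% |
| 0.5 | 0.054 | 1.038 | 21% | 93.1% |
| 1.0 | 0.107 | 1.077 | 41% | 87.3% |

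With half the participants left in every arm (150 versus 70), the half-width is 0.369 log2 and coverage is 94.8%, 94.1% and 91.2%.

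**6. Cost of a cohort term.** In the three-set model, adjusting for cohort adds (0.107)²/S to the variance factor of the 12+16 contrast. S is the within-set sum of squares of the cohort indicator:

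- S = 75 × 225/300 + 75 × 225/300 + 50 × 90/140 = 56.25 + 56.25 + 32.14 = 144.64.
- Unadjusted factor: 1/300 + 1/140 = 0.010476.
- Adjusted factor: 0.010476 + 0.01148/144.64 = 0.010556.
- SE ratio: √(0.010556/0.010476) = 1.0038; the half-width goes from 0.261 to 0.262 log2.

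If only 12+16 and one vaccine-first set are modelled, S = 56.25 + 32.14 = 88.39 and the ratio is 1.0062. For 11a+14 versus 11b+15 the ratio is 1.

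**The case against.** **The main comparison is untouched.** A reader might infer that the Cohort 4 primary comparison is biased. The documents do not support that. The primary objective in Protocol Section 3 concerns groups with and without revaccination, most directly 11a+14 versus 11b+15, and 9.2.4 sizes the study on those arms. No section names a contrast with the placebo-first set as primary. This objection stands and limits the point to the other planned contrasts.

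**The ANOVA may not cover vaccine versus placebo.** Before Day X, Arms 12 and 16 have received only placebo, and the model is worded for active arms. Read literally, it yields no ratio against 12+16 at those visits. The SAP's "the following arms will be combined and compared to each other for all timepoints" points the other way. The ambiguity is real, so it would be too strong to say that the vaccine-versus-placebo contrast is certainly affected. After Day X, 12+16 has been vaccinated and the doubt falls away.

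**The effect may be small.** The cohorts share eligibility criteria, visit schedule, the 1 mL formulation and the revaccination timepoint. The second Day 1 injection in Arms 11a and 11b is saline, a weak reason for titres to differ. At 0.25 to 0.5 log2, coverage barely moves. This stands as to size, but the cohort difference cannot be known in advance.

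**Other safeguards exist.** Baseline titre, age and sex could absorb part of a cohort difference, and the separate 28-day analyses could reveal an early one. But the sensitivity model is optional and omits cohort, and the 28-day analyses do not adjust the later pooled contrasts. Combining arms as applicable gives discretion over pooling; it adds no adjustment.

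**The analysis is descriptive.** No hypothesis is tested, so no type I error claim can be made. The estimates and intervals are the study's inferential output, however, and an avoidable bias in them still matters.

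**Conclusion.** The concern holds for contrasts of 12+16 with 11a+14 or 11b+15: clearly after Day X, and before Day X if the SAP's all-timepoints comparison is taken to include the placebo-first set. The weight, 10.7% of the cohort difference, follows from the planned arm sizes. The resulting bias is not known. Error in the GMR of 1.9% to 7.7% rests on assumed differences of 0.25 to 1.0 log2, and the comparison with the interval width also assumes that the SD of 1.3 carries over to Cohorts 3 and 4. Equal retention across arms and a cohort effect common to all arms are assumed throughout.

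This is a modest, avoidable bias in planned contrasts on the Cohort 4 primary endpoint. It does not undermine the revaccination comparison. It is worth correcting because the correction is nearly free and, once pre-specified, leaves no model choice to be made after the data are seen.

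**What to change.** In SAP 5.3.3, add cohort as a fixed factor to the ANOVA whenever arms from Cohorts 3 and 4 are pooled, and to the covariate-adjusted sensitivity version. Report cohort-adjusted geometric means, evaluated at the same cohort mix for every pooled set, and cohort-adjusted ratios. State in the same place whether 12+16 enters the model before Day X, so that the active-arms and all-timepoints wordings agree.

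The cost is one model term and about 0.4% in standard error for the placebo-first contrasts (0.6% if sets are modelled in pairs), with none for 11a+14 versus 11b+15. Sample size and study conduct do not change. The term removes an additive cohort effect only. If cohort changes the response to vaccine but not the titre under placebo, that interaction remains; showing the ratios by cohort beside the pooled estimate would make it visible.
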